7.7.3 Management of Specific Toxicities

7.7.3.1 Chills, Anaphylaxis, and Hypersensitivity Reactions

Chills associated with SL-401 administration may be treated with meperidine 12.5-50 mg IV or morphine sulphate 1-2 mg IV. Anaphylaxis and hypersensitivity reactions associated with rash, fever, urticaria, bronchospasm, and/or angioedema will be treated with 100 mg IV methylprednisolone (or an equivalent corticosteroid) and 25-50 mg IV diphenhydramine. More severe symptoms will also be treated with 0.3 cc epinephrine (1:1000) IV once. Patients with anaphylactic (grade 4) reactions or ≥ grade 3 hypersensitivity reactions should not receive additional infusions of SL-401.

In the setting of grade 1-2 hypersensitivity reactions, subsequent administration of SL-401 may be attempted, provided that any systemic symptoms of the prior grade 1-2 hypersensitivity reaction resolve within 24 hours with appropriate supportive measures. Premedication for patients with prior grade 1-2 hypersensitivity reactions should include the agents specified in Section 7.3.2.2; additional premedication may be provided at the Investigator's discretion and should be discussed with the study Medical Monitor or designee. Refer to Section 10.7 concerning recommended optimal reporting of SL-401 related hypersensitivity reactions.

Blood (serum) samples (10 mL for immunogenicity) will be collected anytime during the study when clinical manifestations are observed suggesting either an infusion related reaction or drug hypersensitivity.

7.7.3.2 Symptomatic Hypotension

Symptomatic hypotension will be treated with a bolus of 500 cc normal saline and a hold (postponement) on further drug infusion until resolution. During the dosing period, if the BP fails to improve with two 500 cc bolus saline infusions, further standard measures to correct the BP will be undertaken, regardless of the rapidity or delay in resolution, and SL-401 will be withheld on that day. If low BP persists such that further treatment is not feasible during the day of the intended dose and the following day, no further SL-401 will be administered to that patient for that cycle.

7.7.3.3 Capillary Leak Syndrome

Capillary leak syndrome is associated with vascular endothelial injury related to fusion protein administration and may occur 3 – 8 days after initiation of treatment. Patients may exhibit symptoms of hypotension, weight gain, edema, nausea, and anorexia, shortness of breath and, at

times, confusion and muscle injury. Findings may include hypoalbuminemia, reductions in blood oxygen saturation, and evidence of pulmonary edema on chest x-ray. Patients with hypotension will receive 500 cc normal saline boluses and observation as detailed in Section 7.7.3.2. Patients will have serum albumin measurements daily until completion of SL-401 administration and will receive 25 g albumin IV each day the serum albumin is < 3 g/dL. Patients with > 10% weight gain and no hypotension may be treated with fluid restriction and/or diuretics such as furosemide as clinically indicated per Investigator discretion.

As indicated above in the setting of delays secondary to findings consistent with capillary leak syndrome (i.e., in the setting of resolved hypotension, tachycardia, increased weight, or albumin reductions of a magnitude lower than those warranting withholding of SL-401 for the duration of a given cycle), subsequent SL-401 infusions are to be administered on days subsequent to the identification of the abnormality (not the same day), pending determination by the Investigator that there is no/minimal evidence of ongoing capillary leak syndrome and pending discussion with the study Medical Monitor.

In settings in which albumin is reduced to <3.0g/dL or in which albumin is reduced by more than 1.0 g/dL below the level at the start of the cycle (i.e. from 4.3g/dL to 3.2g/dL), no subsequent SL-401 will be administered for the duration of the cycle.

7.8 Guidelines for Initiation of a New Cycle of Therapy

For a new cycle of treatment to begin, the patient must meet the following criteria:

- ANC must be ≥ 1,000/mm³.
- Platelet count must be ≥ 50,000/mm³.
- All other non-hematologic SL-401 related toxicity must have resolved to ≤ grade 1 or to the patient's baseline condition.
- The patient does not have any adverse events that require holding SL-401 (Table 11) or has not had prior anaphylaxis or ≥ grade 3 hypersensitivity reaction.
- All other non-hematologic POM/DEX related toxicity must have resolved to ≤ grade 2 or to the patient's baseline condition.

If the patient fails to meet the above-cited criteria for initiation of the next cycle of treatment, dosing should be delayed for 1 week. At the end of that time, the patient should be re-evaluated to determine whether the criteria have been met. If the patient continues to fail to meet the above-cited criteria, within 14 days from a scheduled day one of therapy, then discontinue treatment. In patients in whom there may be evidence of MM response or stability as determined by the treating physician, treatment may be resumed at a reduced SL-401/POM/DEX dose level after discussion with the Medical Monitor.

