6.2.1 Phase 1: Dose Escalation

Run-In Cycle: SL-401 will be evaluated at doses of 7, 9, or 12 μg/kg/day, for 5 consecutive days (Days 1-5; with postponement as required by adverse events such that 5 doses over 10 days is permitted) as single agent during an initial Run-in Cycle. Upon completion of the Run-in Cycle patients will be evaluated for safety and response.

- Patients who do not experience a DLT during the Run-in Cycle will have POM/DEX added to their regimen at the assigned cohort dose.
- Patients who experience a DLT during the Run-in Cycle will be discontinued from study.

Table 7 details the SL-401/POM/DEX dose levels, beginning with dose level 1 to be evaluated.

Table 7: Dose Levels to be Evaluated

Dose Level	DLT EVALUTION PERIOD = RUN IN CYCLE and CYCLE 1				
	Run-In Cycle	Combination therapy Cycles 1 - 6			
	SL-401(IV) Daily on Days 1 – 5	SL-401(IV) Daily on Days 1 – 5	POM (oral) Daily on Days 1 – 21	DEX (oral) on Days 1, 8, 15 and 22	
-1	5 μg/kg	5 μg/kg	4 mg	40 mg	
1	7 μg/kg	7 μg/kg	4 mg	40 mg	
2	9 μg/kg	9 μg/kg	4 mg	40 mg	
3	12 μg/kg	12 μg/kg	4 mg	40 mg	

Cohorts of 3-6 patients will be treated at each dose level. All patients within a cohort must complete the Run-in Cycle and the first cycle of combination therapy (Cycle 1) before patients can be enrolled into the subsequent cohort of SL-401 (single agent) at the next higher dose. No intra-patient dose escalation is allowed. The first cohort of patients will receive SL-401 single agent at a dose of 7 µg/kg/day followed by SL-401 with POM/DEX. After all patients in this cohort complete the Cycle 1 of therapy, the dose for the second cohort of patients will increase to 9 µg/kg/day, conditional on the DLT rules described below. Similarly, after all patients in the second cohort complete Cycle 1 of therapy, the dose for the third cohort of patients will increase to 12 µg/kg/day, conditional on the DLT rules described below.

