6.2.2 Dose limiting Toxicity Definition

Run-In Cycle

In order to be evaluable for DLT assessment during the Run-in Cycle of single agent SL-401, a patient must receive all 5 doses within a 10 day time period (Days 1 – 10) and complete the 28 days of observation unless they experience DLT (patients who discontinue prior to this juncture because of disease progression or for reasons unrelated to study therapy will be replaced).

Combination Therapy Initial Cycle (Cycle 1)

In order to be evaluable for DLT assessment in Cycle 1 (initial cycle of combination therapy), a patient must receive at least 3 infusions of SL-401 and 16 (approximately 75%) doses of POM during Cycle 1, and complete the 28 days of observation unless they experience DLT. (Patients who discontinue prior to this juncture because of disease progression or for reasons unrelated to study therapy will be replaced).

The period of evaluation for DLT will include Run-in Cycle and Cycle 1 (the initial cycle of combination therapy).

DLT is defined as any of the following treatment-emergent adverse events (TEAEs) that are possibly, probably, or definitely related to therapy occurring in the first cycle:

- Any ≥ grade 4 neutropenia lasting greater than 7 days or ≥ grade 3 neutropenia associated with fever.
- Any grade ≥ 4 thrombocytopenia lasting greater than 7 days or ≥ grade 3 thrombocytopenia associated with bleeding.
- Any ≥ grade 3 non-hematologic toxicity except:
 - Grade 3 nausea, vomiting, or diarrhea lasting no longer than 48 hours (with resolution to ≤ grade 1 or baseline) with optimal supportive care.
 - Grade 3 arthralgia, myalgia, fever, in the absence of neutropenia, lasting no longer than 48 hours (with resolution to ≤ grade 1 or baseline).
 - Grade 3 fatigue lasting < 7 days.
 - Grade 3 laboratory abnormalities that are asymptomatic and not considered clinically significant by the Investigator, that respond to or do not require intervention and resolve to ≤ grade 1 or baseline ≤ 28 days after the last infusion of SL-401.
- Grade 4 transaminase or CPK elevation (confirmed within 24 hours of initial identification) regardless of duration or relationship to SL-401.

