Capillary Leak Syndrome (including suspected capillary leak syndrome) as manifested by hypotension, tachycardia, reduced albumin, or increased weight.		In the setting of delays secondary to findings consistent with capillary leak syndrome (i.e., in the setting of resolved hypotension, tachycardia, increased weight, or albumin reductions of a magnitude lower than those warranting withholding of SL-401 for the duration of a given cycle), subsequent SL-401 infusions are to be administered pending determination by the Investigator that there is no/minimal evidence of ongoing capillary leak syndrome and pending discussion with the study Medical Monitor. Any subsequent SL-401 infusions are to be administered on days subsequent to the identification of the abnormality (i.e., not the same day the abnormality was identified). In settings in which albumin is reduced to <3.0g/dL or in which albumin is reduced by more than 1.0 g/dL below the level at the start of the cycle (i.e. from 4.3g/dL to 3.2g/dL), no subsequent SL-401 will be administered for the duration of the cycle.
Any other grade 3 SL-401 related non-hematologic toxicity.		In the case of arthralgia, myalgia, fever responding to treatment, or nausea, vomiting and diarrhea with suboptimal treatment or reversible lab abnormalities, implement supportive care and resume at same dose if resolved to ≤ grade 1 or baseline and complete the scheduled cycle (up to 5 doses over 10 days if feasible). If not resolved by Day 1 of subsequent cycle, monitor weekly or more frequently if appropriate. Resume at one level dose reduction when resolved to ≤ grade 1.
		If treatment is held for more than 14 days of planned start of subsequent cycle, discontinue study drug.
		Additional options may be pursued following discussion with the Medical Monitor for patients with evidence of MM stabilization/response.
Any grade 4 SL-401 related non-hematologic toxicity.		Consider permanent discontinuation of therapy. Additional options may be pursued following discussion with the Medical Monitor for patients with evidence of MM stabilization or response.
SL-401 Adverse events that requi	re specific manage	ment
Chills, Anaphylaxis and Hypersensitivity Reaction		Refer to Section 7.7.3.1
Symptomatic hypotension		Refer to Section 7.7.3.2
Capillary leak syndrome		Refer to Section 7.7.3.3
Pomalidomide		
Rash Grade 2 or 3		Hold POM. Follow weekly.

CTCAE Category	Agents	Toxicity During a Cycle

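### Section 7.8 lets a responding or stable patient resume SL-401 at a reduced dose without excluding the severe hypersensitivity reactions after which Section 7.7.3.1 bars the drug

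*Protocol*

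**What the plan says.** **The bar.** Section 7.7.3.1 states: "Patients with anaphylactic (grade 4) reactions or ≥ grade 3 hypersensitivity reactions should not receive additional infusions of SL-401". It allows another attempt after grade 1-2 reactions under stated conditions and makes no exception for disease response. Table 11 (Section 7.7.2) has a row headed "Chills, Anaphylaxis and Hypersensitivity Reaction" that refers the reader to 7.7.3.1.

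**The cycle-start rule.** Section 7.8 lists the conditions for a new cycle. The fourth is worded as follows: "does not have any adverse events that require holding SL-401 (Table 11) or has not had prior anaphylaxis or ≥ grade 3 hypersensitivity reaction". A patient who fails the list is delayed one week and re-evaluated. The default is then: "If the patient continues to fail to meet the above-cited criteria, within 14 days from a scheduled day one of therapy, then discontinue treatment".

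**The exception.** The next and last sentence of 7.8 begins "In patients in whom there may be evidence of MM response or stability as determined by the treating physician" and goes on to say that "treatment may be resumed at a reduced SL-401/POM/DEX dose level after discussion with the Medical Monitor".

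**Discontinuation.** Section 7.9.1 lists SL-401-related anaphylaxis or hypersensitivity of grade 3 or higher among the reasons for stopping SL-401, but only as a reason for which treatment *may* be stopped.

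**The concern.** Severe hypersensitivity to the investigational drug needs a single answer on rechallenge. The default in 7.8 agrees with 7.7.3.1: no further drug. The closing sentence of 7.8 does not. It applies to patients who failed the criteria just listed, one of which names prior anaphylaxis. It offers a reduced dose of a regimen that explicitly includes SL-401, and it excludes none of the criteria.

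The patients affected are those responding or stable after a severe reaction, for whom the wish to continue is strongest. For them one section says stop and the other says a reduced dose may be discussed.

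The *or* in the fourth condition is a secondary drafting error. It can make the criterion appear to be met before the closing sentence is reached.

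**Working it through.** The plan states no figure on this point. The check compares the rules, tests the logic of the fourth condition, and counts where the conflict can arise.

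**1. Following one patient through 7.8.** Take a patient who had a grade 3 hypersensitivity reaction in Cycle 2, has recovered, and has stable disease.

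- *Criterion, intended reading:* failed, because of the prior reaction.
- *One-week delay and re-evaluation:* no change. A prior reaction is history and cannot resolve.
- *Default:* discontinue. This agrees with 7.7.3.1.
- *Closing sentence:* resume at a reduced dose after discussion with the Medical Monitor. This contradicts 7.7.3.1.

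Correcting the *or* therefore does not close the gap. The patient fails the corrected criterion permanently, and the closing sentence still offers a way back to SL-401.

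**2. Logic of the fourth condition.** Let A be a current event requiring a hold of SL-401 and B a prior severe reaction.

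| A | B | As written: not A *or* not B | Intended: not A *and* not B |
|---|---|---|---|
| no | no | pass | pass |
| no | yes | pass | fail |
| yes | no | pass | fail |
| yes | yes | fail | fail |

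The written form gives the wrong result in both mixed rows. It passes a patient with prior anaphylaxis and no current hold event, and a patient with a current hold event and no prior reaction.

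**3. Does neighbouring text settle it?** Not expressly.

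- Section 7.8 neither cites 7.7.3.1 nor says that it prevails.
- Section 7.9.1 is permissive.
- The Table 11 row for grade 4 SL-401-related non-hematologic toxicity asks only that permanent discontinuation be considered. It allows other options for responding or stable patients, again without excluding anaphylaxis.

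**4. Where it can arise.**

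- *Phase 1:* a Run-in reaction drops out. The DLT definition in 6.2.2 covers "Any ≥ grade 3 non-hematologic toxicity except" for listed exceptions that do not include hypersensitivity, and 6.2.1 adds: "Patients who experience a DLT during the Run-in Cycle will be discontinued from study". Section 7.7 lets a patient with a Cycle 1 DLT continue if the toxicity can be managed, so such a patient can reach the Cycle 2 start. Planned cycle starts after a reaction: 6 − 1 = 5 (Cycles 2 to 6).
- *Phase 2:* there is no Run-in and first exposure is in Cycle 1, so again 6 − 1 = 5.
- *Beyond Cycle 6:* SL-401 is given every other cycle (Table 13, note u), so further starts are possible but sparser.

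**5. What a reduced dose means.** One step in Table 8:

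- 12 to 9 µg/kg: 9/12 = 75% of the prior dose
- 9 to 7 µg/kg: 7/9 = 78%
- 7 to 5 µg/kg: 5/7 = 71%
- 5 µg/kg: no lower step

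**6. How often.** Table 6 reports 1 attributed anaphylaxis of grade 3 or higher among 92 patients in the earlier study: 1/92 = 1.1%. That study was designed around a single cycle, so the figure suggests a small group but does not measure risk over repeated cycles.

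**The case against.** The best reply is that the protocol has already decided the question. Section 7.7.3.1 grades rechallenge explicitly, Table 11 points to it, and a specific rule naturally governs a general sentence that never mentions the reaction. The closing paragraph of 7.8, with its one-week delay and 14-day limit, reads as a provision for slow recovery from toxicities that can resolve. The row in Table 11 for other grade 3 SL-401-related toxicity follows much the same sequence. Resumption is optional and requires the Medical Monitor, who would have 7.7.3.1 at hand. On this view only a cross-reference is missing. The dose ratios and cycle counts also do not measure harm.

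Much of this stands. A careful reader would probably apply the bar, and 7.8 does not override 7.7.3.1 or independently authorise re-dosing. The dose ratios and cycle counts describe the scope of the conflict and say nothing about risk.

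It does not remove the conflict. The 7.8 list itself names prior anaphylaxis, so the exception that follows failure of that list reaches it. Nothing says which section prevails, and two other provisions (7.9.1 and the grade 4 row of Table 11) are permissive in the same direction. A safety bar should not depend on the reader choosing the right rule of interpretation.

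**Conclusion.** The concern holds: Section 7.8 is wrong as written and should be fixed. Its closing sentence conflicts with the bar in 7.7.3.1, and the *or* in its fourth condition is a drafting error.

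The scope is narrow. It concerns patients with anaphylaxis or a hypersensitivity reaction of grade 3 or higher from Cycle 1 onward who remain on study with possible response or stability. No rate of wrongful re-dosing can be derived from the document, and none is claimed. Power, sample size and error rates are untouched.

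The conclusion assumes that 7.7.3.1 states the intended rule, which the Table 11 pointer supports. It also takes the closing sentence of 7.8 at its word, as applying to any failed criterion.

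**What to change.** In Section 7.8:

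- Replace the fourth condition with two that must each be met: (a) no current adverse event requiring a hold of SL-401 under Table 11; (b) no prior anaphylaxis or hypersensitivity reaction of grade 3 or higher to SL-401.
- Add to the closing paragraph: *The delay and resume provisions do not apply to SL-401 in patients with prior anaphylaxis or grade ≥3 hypersensitivity reaction, who receive no further SL-401 (Section 7.7.3.1).*

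For consistency, make the matching item in Section 7.9.1 mandatory and add the same exclusion to the grade 4 row of Table 11.

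The cost is a wording amendment, with no added procedures, visits or patients.

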5.4 Replacement of Patients

At the discretion of the Sponsor, additional patients may be enrolled to supplement patient data compromised due to premature study dropout or other reasons. During phase 1, patients who discontinue the study prior to completing the DLT evaluation period because of disease progression or for reasons unrelated to study therapy will be replaced. All patients in phase 2

and those treated at the MTD or recommended phase 2 dose as established in phase 1, who are not evaluable for response will be replaced.

6 Investigational Plan

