In the event that 2 patients within a cohort have a DLT, then the MTD will be exceeded and further dose escalation will not occur. The MTD is defined as the dose preceding the dose level at which 2 patients experience a DLT. The MTD will be used in phase 2 of the study. If the highest planned treatment dose is completed and determined to be safe and the MTD is not exceeded, the available PK and safety data will be reviewed to assess whether further dose escalation is justified. A patient who does not complete the first 2 cycles of treatment for reasons other than the occurrence of DLT will be replaced by another patient who will receive the same dose regimen if necessary to evaluate that cohort (e.g., if a patient is not evaluable for DLT but 2 others have experienced a DLT within the cohort, there will be no need to replace the patient as the MTD will have been exceeded).

In the event that a DLT occurs in 2 patients treated at the 7 µg/kg/day dose level, 5µg/kg/day may be considered by the DSRC as an alternative starting dose. In this event, a new cohort of 3 patients will receive 5 µg/kg/day including a single agent Run-in Cycle prior to the first cycle of combination therapy. The same DLT rules will apply to this dose level. If 2 or more patients experience a DLT at the 5 µg/kg/day dose level, the study will be halted.

SL-401 related toxicities are AEs that are considered by the Investigator to be either possibly, probably or definitely related to investigational SL-401. (Refer to Section 10.6 for more thorough guidance as to the assessment of "relatedness" in the context of investigational anticancer therapy). It should be noted that although the cycle length is 28 days, cycle duration may extend beyond 28 days in the setting of AEs, which are detailed in Section 7.7.2.

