7.7 Dose Modifications

Patients will be evaluated for AEs at each visit, with the NCI CTCAE, v.4.03, used as a guide for the grading of severity.

During the Run-in Cycle and Cycle 1 of combination therapy of phase 1, doses of SL-401 may be held per criteria detailed in Section 7.7.2.2, Section 7.7.2.3, and Table 11. In the setting of these criteria, 5 doses may be given over 10 days; otherwise no dose modifications are permitted during the Run-in Cycle and Cycle 1 of combination therapy unless the patient experiences a DLT. No dose escalations are permitted in any given patient once a dose level has been assigned. While patients experiencing DLT during Cycle 1 of combination therapy may continue on therapy, if toxicity can be managed according to the dose modification guidelines outlined below, the DLT event will contribute to the assessment of MTD for that given cohort.

Dose modifications may be performed in all subsequent cycles of treatment. If toxicities cannot be managed by dose modification or the patient cannot tolerate the lowest dose of study drug, the patient is to be discontinued from study drug unless there is evidence of clinical benefit beyond the initial treatment cycle. However, patients who have achieved disease control while receiving study therapy will continue to adhere to the schedule of assessments followed during the treatment phase of the study even though study drug has been discontinued.

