11.2 Populations for Analysis

11.2.1 Phase 1 (Evaluable for Toxicity)

Patients will be considered evaluable for toxicity if they receive any study drug. Patients will be considered evaluable for dose limiting toxicity if they receive any study drug and are followed for the full 2 cycles or experience a DLT prior to completion of 2 cycles. All patients who are not evaluable for DLT will be replaced.

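### Phase 1: a patient who cannot start Cycle 1 within 14 days because of treatment-related toxicity that is not a listed DLT is stopped and replaced, so the event never enters the count that sets the MTD

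*Protocol*

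**What the plan says.** **Restart rule.** Protocol Section 7.8 requires ANC of at least 1,000/mm³, platelets of at least 50,000/mm³ and SL-401-related non-hematologic toxicity back to grade 1 or baseline before any new cycle. After a first one-week delay it states: "If the patient continues to fail to meet the above-cited criteria, within 14 days from a scheduled day one of therapy, then discontinue treatment". For patients with possible response or stability it adds that "treatment may be resumed at a reduced SL-401/POM/DEX dose level after discussion with the Medical Monitor". Phase 1 Cycle 1 is not excepted. Section 9.2.6 expects that Cycle 1 may be delayed after the Run-in Cycle.

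**Cycle 1 dose.** Section 6.2.1: "Patients who do not experience a DLT during the Run-in Cycle will have POM/DEX added to their regimen at the assigned cohort dose". Section 7.7, after allowing SL-401 infusions to be held: "otherwise no dose modifications are permitted during the Run-in Cycle and Cycle 1 of combination therapy unless the patient experiences a DLT". The synopsis repeats this, and Table 13 footnote q places dose modification after the Run-in Cycle and Cycle 1.

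**DLT and evaluability.** The hematologic DLTs in Section 6.2.2 are grade 4 neutropenia or thrombocytopenia for more than 7 days, grade 3 or higher neutropenia with fever, and grade 3 or higher thrombocytopenia with bleeding. No item concerns delay. For Cycle 1 evaluability, "a patient must receive at least 3 infusions of SL-401 and 16 (approximately 75%) doses of POM during Cycle 1"; the dose level is not mentioned.

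**Replacement.** Section 6.2.1: "A patient who does not complete the first 2 cycles of treatment for reasons other than the occurrence of DLT will be replaced". Section 11.2.1: "All patients who are not evaluable for DLT will be replaced". Section 5.4 instead says that phase 1 patients who leave before the end of the DLT window "because of disease progression or for reasons unrelated to study therapy will be replaced", and Section 6.2.2 uses the same two grounds.

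**The concern.** The MTD is a primary objective and becomes the phase 2 dose. It is set by counting patients with a DLT in the Run-in Cycle and Cycle 1, in cohorts of 3 to 6. A patient whom SL-401 toxicity keeps from receiving the combination at all is informative about tolerability. As written, that patient can leave the cohort without trace and be succeeded by someone who tolerated the Run-in Cycle.

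Two further gaps lie at the same step. The replacement sections give different grounds, so sites and sponsor could treat identical patients differently. And Section 7.8, read alone, lets a site start Cycle 1 below the cohort dose, while Section 6.2.2 would still accept that patient as evaluable for the cohort.

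**Working it through.** The protocol states no target DLT rate and no operating characteristics, so there is no planned figure to reproduce. The check is a trace of the rules, followed by an illustration.

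**Rule trace.** Take a patient at 9 µg/kg/day with no Run-in DLT and ANC 800 without fever until 20 days after the scheduled Cycle 1 Day 1.

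1. Section 7.8 blocks Cycle 1, because 800 is below 1,000.
2. Growth factors are barred at this stage without a DLT (Sections 7.2.3 and 7.2.4).
3. There is no DLT under 6.2.2: ANC 800 is not grade 4 (Table 11 puts grade 4 below 500) and there is no fever. Duration does not change this.
4. At 14 days Section 7.8 discontinues the patient. Sections 6.2.1 and 11.2.1 then replace the patient. The DLT contribution is 0.
5. If the reduced-level option were used instead, SL-401 would drop to 7 µg/kg (Table 8). Five infusions and 21 POM doses would satisfy 6.2.2, giving one evaluable non-DLT patient for the 9 µg/kg cohort.

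With two other patients free of DLT and a DLT-free replacement, the cohort reads 0/3 and escalates to 12 µg/kg. If the stop counted as a DLT, it would read 1/3 and expand to 6.

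**A contrast within 6.2.2.** An asymptomatic grade 3 laboratory abnormality under the non-hematologic item escapes DLT status only if it resolves within 28 days of the last infusion. With the last infusion on Day 5 to Day 10, that is Day 33 to Day 38. Cycle 1 is due about Day 29, so a delay of more than 14 days means low counts beyond Day 29 + 14 = Day 43. Persistence matters for the one kind of toxicity but not for uncomplicated grade 3 cytopenia.

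**Illustration.** The 3+3 rule in Section 6.2.1 escalates on 0/3, or on 1/3 followed by 0/3. With per-patient probability r of a counted DLT:

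P(escalate) = (1 − r)³ + 3r(1 − r)⁵

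Assumptions: DLT rate p = 0.20; rate q of delays over 14 days without a DLT; the two are mutually exclusive.

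- Replaced: r = p/(1 − q)
- Counted as a DLT: r = p + q
- Reduced level, scored non-DLT: r = p = 0.200, giving 0.512 + 0.197 = 0.709

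| q | r replaced | P replaced | r counted | P counted | Difference |
|---|---|---|---|---|---|
| 0.022 | 0.204 | 0.699 | 0.222 | 0.661 | 0.038 |
| 0.050 | 0.211 | 0.686 | 0.250 | 0.600 | 0.086 |
| 0.087 | 0.219 | 0.667 | 0.287 | 0.521 | 0.146 |

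The end values of q are borrowed from Table 6 (Section 3.5.3): grade 3 or higher neutropenia 2/92 = 2.2% and thrombocytopenia 8/92 = 8.7%. They are not delay rates. They cover events of any duration, across two regimens and doses from 4 to 22.12 µg/kg/day, in AML, MDS, CML and BPDCN. They probably overstate long delays from low counts. On the other side, they leave out grade 2 SL-401-related non-hematologic toxicity, which also blocks a new cycle under 7.8.

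**The case against.** **The specific rule governs Cycle 1 dosing.** Section 7.7, the synopsis and footnote q all bar modification in Cycle 1 without a DLT, while 7.8 is general and permissive. Its wording also presumes a patient already on the combination, and POM/DEX has not started at this step. This largely stands. A reader might infer that the plan intends patients at 7 µg/kg to be scored for the 9 µg/kg cohort; the documents do not support that. The reduced-level sentence is a wording conflict to close. Discontinuation and replacement remain.

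**Sections 5.4 and 6.2.2 do not forbid other replacements.** Correct: neither says that its two grounds are exclusive, and 5.4 opens by letting the sponsor add patients for dropout or other reasons. So the sections differ in breadth; 5.4 does not prohibit what 6.2.1 requires. On no reading does the stop become a DLT.

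**The review committee sees this.** The DSRC must evaluate laboratory abnormalities and each dose level before escalation. At least 6 patients must be evaluated to confirm the MTD, and the first 6 phase 2 patients are assessed for DLT again. These are real safeguards. They do not alter the written count: 0/3 still escalates, and the MTD is still defined by DLTs.

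**Counting delay as a DLT is a design choice.** Partly so. Patients may enter at ANC 1,000 and platelets 50,000/µl, the same thresholds that block a cycle, and Section 7.7.2 handles disease-related cytopenia case by case. This is a reason to confine the rule to treatment-related toxicity.

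**The direction depends on the comparator.** Also true. Against counting the patient as a DLT, replacement raises the chance of escalation. Against scoring the patient as non-DLT, it lowers it (0.667 against 0.709 at q = 0.087).

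**Conclusion.** The point holds for discontinuation and replacement. A treatment-related stop before Cycle 1 that is not a listed DLT adds nothing to the count that sets the MTD, and the four sections on replacement do not agree on its grounds. The reduced-level sentence in 7.8 conflicts with 7.7, the synopsis and footnote q, and the evaluability rule in 6.2.2 does not guard against it.

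The size is unknown, because the documents give no rate of such delays. At an assumed 20% DLT rate and 2.2% delay rate, the chance of escalation is about 70% with replacement and 66% if the patient is counted. The wider gap at 8.7% (67% against 52%) might be read as the expected effect. It should not be: that rate is for events of any severity from grade 3 and any duration, in other diseases and at other doses. What does not depend on the rate is that, in a cohort of 3, one such patient decides between 0/3 and 1/3. The text should be corrected, but the point does not undermine the dose-escalation design as a whole.

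**What to change.** 1. In Section 7.8, state that the reduced-dose option does not apply to the start of Cycle 1 in phase 1. In Section 6.2.2, require the Cycle 1 SL-401 infusions and POM doses to be given at the assigned cohort level for DLT evaluability.
2. Give Sections 5.4, 6.2.1, 6.2.2 and 11.2.1 one replacement rule: only patients who stop for progression or for reasons unrelated to study therapy are replaced. A patient who cannot start Cycle 1 within the 14-day allowance, or cannot complete it, because of treatment-related toxicity counts as a DLT and is not replaced. Add this to the DLT list in 6.2.2 and to the matching synopsis text.

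The cost is a few sentences in a protocol amendment and no additional data. A cohort may expand from 3 to 6 patients; three levels of 6 remain within the planned maximum of 18. The trade-off is a somewhat more cautious escalation, limited by the requirement that the toxicity be treatment-related.
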